### **9.5 Data Analyses**

#### **Primary analysis**

We will first confirm that the residuals of seated blood pressure are normally distributed (if not then it will be log-transformed). We will compare net effect of reduced sodium versus usual diet on 2-week seated blood pressure. This comparison will be performed by fitting a linear regression with adjustment for baseline seated blood pressure. We will perform an intent-to-treat analysis.

Our hypothesis is that 2-weeks of low sodium dietary intervention will lower seated blood pressure compared to 2-weeks of usual sodium diet. The null hypothesis is that there will be no difference in seated blood pressure between the two intervention arms. The comparison between the two treatment groups will be performed by comparing the regression coefficient for treatment with zero (two-sided Wald test at 0.05 significance level).

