3.1 Randomization and primary analysis

Participants will be randomized using a computer-generated randomization scheme with varying sized blocks to 1 of 2 meal plans in a 1:1 ratio such that approximately half of participants will undergo the low sodium diet intervention, while the other half will undergo the usual sodium meal plan intervention. Sex will be used as a stratification variable to ensure that sex is evenly distributed between interventions.

We will first confirm that the residuals of seated blood pressure are normally distributed (if not then it will be log-transformed). We will compare net effect of reduced sodium versus usual diet on 2-week seated blood pressure. This comparison will be performed by fitting a linear regression model with adjustment for baseline seated blood pressure. We will perform an intent-to-treat analysis.

Our hypothesis is that 2-weeks of a low sodium meal plan intervention will lower seated blood pressure compared to 2-weeks of a usual sodium diet. The null hypothesis is that there will be no difference in seated blood pressure between the two intervention arms. The comparison between the two treatment groups will be performed by comparing the regression coefficient for treatment with zero (two-sided Wald test at 0.25 significance level to avoid type II error)¹ using linear regression with adjustment for baseline blood pressure.

Our primary outcome will be the average of two systolic blood pressures measured on days 12-15 of the study period. A sensitivity analysis will be performed examining the last systolic blood pressure measurement.

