3.2 Power and sample size

To detect the 2-week difference in seated SBP (primary outcome) observed in the DASH-Sodium trial² (-9.53 mm Hg, standard deviation of 10.46, a type 1 error of 0.05 with 80% power), we need 20 people in each arm (total 40). We will recruit 45 participants to account for a 10% attrition rate. Effect size and variance for the other endpoints (especially OH) will be used to inform power calculations for subsequent proposals.

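### The primary test is set at two-sided 0.25 in the SAP but at two-sided 0.05 in the protocol, and both sample-size statements rest on 0.05

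*SAP*

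**What the plan says.** Both documents describe the same primary analysis: a linear regression of 2-week seated blood pressure on treatment, adjusted for baseline, with the treatment coefficient tested against zero. They differ on the level of that test.

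- Protocol 9.5, Primary analysis: "two-sided Wald test at 0.05 significance level".
- SAP 3.1: "two-sided Wald test at 0.25 significance level to avoid type II error", followed by a citation to a paper on planning pilot studies, and carried out "using linear regression with adjustment for baseline blood pressure".
- SAP 3.2, for the same outcome: "a type 1 error of 0.05 with 80% power". Protocol 9.2 gives the same error rate and power.

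Both sample-size statements take a difference and spread of "9.53 mm Hg, standard deviation of 10.46" from the DASH-Sodium trial, arrive at 20 per arm, and recruit 45 to allow for 10% attrition.

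Both texts are current. The SAP is dated October 29, 2019, and the protocol's version list records submission of the protocol and final SAP to the IRB on that day. Protocol 9.1 refers the reader to the SAP for further detail but does not say which document prevails if they disagree.

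**The concern.** The threshold that decides the primary hypothesis has two values. The conflict lies between the protocol and the SAP, and also inside the SAP, between 3.1 and 3.2. Of the four places that state an error rate, three say 0.05 and one says 0.25.

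A p-value between 0.05 and 0.25 would support a claim that sodium reduction changes seated blood pressure under the SAP, and would leave the null standing under the protocol. If this is still open when results are seen, the governing rule can be chosen afterwards. SAP 3.3 repeats the primary analysis in subpopulations without giving a level of its own, so the ambiguity may carry over to those tests.

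**Working it through.** **Inputs.** Difference 9.53 mm Hg, SD 10.46, type 1 error 0.05, power 80%, 20 per arm, 10% attrition (protocol 9.2, SAP 3.2); 1:1 allocation (protocol 9.2.1, SAP 3.1); no interim analyses (protocol 9.3), so the whole error rate is spent on one test. The sample-size statements do not say whether 0.05 is one- or two-sided.

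**Step 1: reproduce the stated size.** Normal approximation, n per arm = 2 × [SD × (z for alpha + z for power) / difference]².
- Two-sided 0.05: 2 × [10.46 × (1.960 + 0.842) / 9.53]² = 18.9, so 19 per arm.
- Exact two-sample t (noncentral t): power is 0.780 with 19 per arm and 0.802 with 20, so 20 per arm.
- One-sided 0.05: 2 × [10.46 × (1.645 + 0.842) / 9.53]² = 14.9, so 15 per arm. This does not match.
- Attrition: 40 / 0.90 = 44.4, rounded up to 45. This matches.

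The stated 20 per arm and 45 recruited therefore follow from two-sided 0.05.

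**Step 2: put 0.25 through the same formulas.** Normal approximation: 2 × [10.46 × (1.150 + 0.842) / 9.53]² = 9.6, so 10 per arm. The exact t gives power 0.803 with 10 per arm.

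| Quantity | Two-sided 0.05 | Two-sided 0.25 |
|---|---|---|
| Power for 9.53 mm Hg, 20 per arm (exact t) | 0.802 | 0.956 |
| Per arm for 80% power (exact t) | 20 | 10 |
| Type I error, both directions | 5% | 25% |
| Type I error, each direction | 2.5% | 12.5% |
| Smallest significant difference, unadjusted t | 6.7 mm Hg | 3.9 mm Hg |

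**Step 3: the last row.** Standard error = 10.46 × √(2/20) = 3.308. With 38 degrees of freedom the critical values are 2.024 and 1.168. So 2.024 × 3.308 = 6.70 and 1.168 × 3.308 = 3.86 mm Hg. These limits belong to an unadjusted comparison, not to the planned baseline-adjusted regression. As an illustration, if 10.46 were the SD at follow-up and its correlation with baseline were 0.5 (both assumptions), both limits would be multiplied by √(1 − 0.25) = 0.866, giving about 5.8 and 3.3 mm Hg.

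**Step 4: error rate of the adjusted regression.** A simulation under no effect (40,000 runs, 20 per arm, assumed baseline correlation 0.5) rejected 25.3% of the time at the 0.25 level with t critical values and 26.0% with normal ones. At 0.05 the rates were 5.0% and 5.7%.

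**Step 5: how often the two rules disagree.** They disagree when p lies between 0.05 and 0.25. Under no effect the probability is 0.25 − 0.05 = 20%. Under the design effect it is 0.956 − 0.802 = about 15%.

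**The case against.** The best defence is that 0.25 is a deliberate pilot choice. SAP 3.1 gives a reason and a pilot-planning citation, and the protocol synopsis calls the study a pilot meant to inform a longer trial. The reason is also true as far as it goes: at the design effect, type II error falls from about 20% to about 4%. The gain is larger if the true effect is smaller than the one borrowed from DASH-Sodium. With the same SD and 20 per arm, power at 0.05 and at 0.25 is 0.31 and 0.64 for an assumed 5 mm Hg, and 0.54 and 0.83 for an assumed 7 mm Hg. A reader might conclude that the SAP's reason is false or that 0.25 is a typing error. The documents support neither reading.

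A reader might also infer that an inert diet would be called effective or harmful one time in four. The 25% pools two directions. A false finding of lowering, which is the stated hypothesis, occurs 12.5% of the time, and neither document defines a verdict of harm from this test.

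Finally, the documents set no order of precedence, so keeping 0.25 with matching text throughout would also remove the contradiction.

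The defence does not dispose of the conflict. Both documents still present seated blood pressure as the primary aim with a formal hypothesis, neither calls the 0.25 test a screen or gives a progression rule, and the power statement in the SAP itself is computed at another level.

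**Conclusion.** The point stands as an unreconciled contradiction in the decision rule for the primary outcome, and it should be settled before analysis. The planned size corresponds to two-sided 0.05. Using 0.25 instead multiplies the false-positive rate by five, from 5% to 25% over both directions, and makes the stated 80% power wrong (about 96%). For the effect the trial was sized to detect, the relaxed level is not needed, because 80% power is already available at 0.05.

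The power figures rest on the documents' difference and SD and a two-sample t-test. The documents do not say what the SD of 10.46 represents, so the range of roughly 3.9 to 6.7 mm Hg in which the two rules disagree is approximate, and baseline adjustment would shift both limits. The 5% and 25% error rates do not depend on the SD.

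**What to change.** State one level for the primary test in both documents. The simplest change is to set SAP 3.1 to two-sided 0.05, which matches protocol 9.5, protocol 9.2 and SAP 3.2, and to report the treatment estimate with a 95% confidence interval. Add the word two-sided to both sample-size statements.

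If the team wants 0.25, it should be labelled in both documents as a go/no-go screen for proceeding to the larger trial, kept separate from the test of the primary hypothesis, with power stated at that level (about 96% for 9.53 mm Hg with 20 per arm).

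The cost of the simple fix is one number in the SAP. Sample size and stated power do not change. The downside is that some results, those with p between 0.05 and 0.25, could no longer be called significant.

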## **6 STUDY PROCEDURES**

## 6.1 Schedule of Evaluations

Assessment	Prescreening (by phone)	Screening: Visit-1 (Day-14 to Day -1)	Baseline, Enrollment, Randomization: Visit 2 (Day 0)	Run In Visit 3 (Day - 1 to Day -2)	Treatment Visit 4 (Day 7)	Treatment Visit 5 (Day 10-13)	Follow-up: Final Visit 6 (Day 14)
Medical History	X						
MoCA		X					
Seated blood pressure alone		X		X		X	X
Orthostatic hypotension		X					X
Informed Consent		X					
Demographics		X					
Physical Activity		X					
Medications		X	X				X
Height		X					
Weight		X	X				X
TUG			X				X
Urine collection			X				X
Compliance and Palatability					X		X
Symptoms/Adverse Events			X		X		X
Compliance Calendar			each day of feeding ----- >				

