### **6.2.3 Follow-up Visits**

- **Visit 4 [Telephone Visit (TV), Day 7]:**
  - *Diet adequacy for caloric needs*
  - *Compliance*
  - *Palatability*
  - *Symptoms and Adverse Events*
- **Visit 5 (Intermediate Visit), Day 11-13:**
  - *Seated blood pressure*

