### 7.3 Adverse Events and Serious Adverse Events

**Adverse Event (AE):** any untoward or unfavorable medical occurrence in a participant, temporally associated with the participants' involvement in research (i.e., after RV), whether or not considered related to participation in the research, including:

- New disease diagnosis or illness
- Worsening of pre-existing disease or illness
- New or worsening symptom or sign

**Serious Adverse Event (SAE):** an adverse event that meets 1 or more of these criteria:

- Results in death
- Requires or prolongs hospitalization
- Is life threatening
- Results in persistent or significant disability or incapacity
- Results in congenital abnormality or birth defect
- Is a condition which the investigator judges to represent a significant hazard

- Is a SOTRUE-specific serious adverse event:
    - A fall event
    - An allergic reaction
    - Extremely high or low blood pressure measurements or high pulse rate\*
      - Systolic blood pressure >180 mm Hg
      - Systolic blood pressure < 90 mm Hg
      - Diastolic blood pressure >110 mm Hg
      - Diastolic blood pressure < 40 mm Hg
      - Pulse rate > 120 beats per minute
- \*Low blood pressures may require discontinuation of the study intervention.

In the current project, no laboratory values are collected to assess safety.

During the screening, run-in, intervention day 10-13, and follow up visits participants will have their blood pressure checked. An algorithm will be followed by the research assistant for persons with abnormal blood pressures to refer them to appropriate healthcare, and to notify the study physician(s). At the baseline, telephone, and follow up visits information will be collected from participants about any adverse events, which will be reported to the study physician(s).

Solicited adverse events include uncomfortable fullness, hunger, bloating, constipation, diarrhea, excessive thirst, fatigue, headache, lightheadedness with standing, nausea, falls, falls with injury, allergic reactions (including food related), and any hospitalizations. Additionally, the participant may contact the study physician by phone in the event of a fall or serious adverse event (hospitalization).

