### **9.4 Outcomes**

#### **9.4.1 Primary outcome**

Seated systolic blood pressure measured during the follow-up visit.

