4.2 Secondary Endpoints

We will examine the effect of the low sodium diet on the following additional outcomes, testing the null hypothesis that there is no difference in the following outcomes between the low sodium diet and usual sodium diet intervention. We will examine the distribution of all variables. We will use linear regression for normally distributed outcomes and logistic regression for binary outcomes with and without adjustment for baseline. Continuous variables with non-normal residuals will be log-transformed with effects reported as a % change. If residuals are still not normally distributed even after log transformation we will apply non-parametric approaches.

- A. Seated diastolic blood pressure (average of two measurements days 12 and 14)
 - Continuous variable, normal distribution; as a sensitivity we will also examine last diastolic blood pressure measurement alone
- B. Standing blood pressure
 - Continuous variable, normal distribution

- C. Orthostatic hypotension
 - Binary variable, binomial distribution
- D. Timed Up and Go Test
 - Continuous variable, normal distribution
- E. Urinary sodium concentration, potassium concentration, sodium/creatinine ratio, potassium/creatinine ratio, and sodium/potassium ratio
 - These may require log-transformation; anticipate continuous variables, normal distribution
- F. Orthostatic symptoms
 - Binary variables (severe vs not), binomial distribution
- G. Side effects (5-point Likert scale)
 - Depending on the distribution of responses, side effect data will be analyzed as a continuous variable or dichotomized (none or any symptoms)

5 Missing data

We will employ a number of recommended strategies to prevent missing data:

- A simplified data collection schedule that minimizes participant burden;
- Intention-to-treat analysis that includes following participants according to the data collection schedule regardless of compliance with the study intervention;
- Frequent engagement with the participants through visit reminder calls or notes;
- A 24-hour phone number that participants can contact for questions and support;
- Contiguous windows of time during which specific follow-up visits are allowed;
- Monetary incentives to encourage enrollment and continued participation;
- Rigorous training of clinic staff emphasizing the importance of
 - Positive and warm interpersonal relationships between the participants and study staff

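### SAP 3.1 averages two SBPs from two visits but has no rule for a participant with only one reading, who can be lost from the primary analysis

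*SAP*

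**What the plan says.** SAP 3.1 defines the outcome: "Our primary outcome will be the average of two systolic blood pressures measured on days 12-15 of the study period". It compares the arms by linear regression adjusted for baseline and adds: "We will perform an intent-to-treat analysis". A sensitivity analysis uses the last SBP alone.

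The two readings belong to different visits. Protocol 6.1 schedules seated BP at Visit 5 and at Visit 6 (Day 14), and SAP 4.2 describes the matching diastolic outcome as "Seated diastolic blood pressure (average of two measurements days 12 and 14". Protocol 9.4.1 has a one-visit outcome instead: "Seated systolic blood pressure measured during the follow-up visit".

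The timing of Visit 5 varies. The schedule in Protocol 6.1 reads "Treatment Visit 5 (Day 10-13", Protocol 6.2.3 reads "Visit 5 (Intermediate Visit), Day 11-13", and Protocol 7.2 places a BP check at day 10.

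On missing data, SAP section 5 lists multiple imputation, best- and worst-case scenarios and dropout as an endpoint, all as sensitivity analyses to set against the primary result. It also compares baseline characteristics of complete cases with those of people who have missing measures. On numbers, SAP 3.2 needs 40 and says: "We will recruit 45 participants to account for a 10% attrition rate".

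On stopping the diet, Protocol 7.3 says: "Low blood pressures may require discontinuation of the study intervention". Protocol 6.3 and section 8 encourage continued follow-up after stopping, and SAP section 5 plans to keep collecting data.

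**The concern.** A regression on a two-reading average needs both readings. If one is absent, the outcome is undefined unless the plan supplies a rule, and it supplies none. The natural default is to omit the person, even though a valid post-randomisation SBP is in the database. The alternative is a rule chosen after the data are seen, which is an unplanned decision inside the primary analysis. Stating intent-to-treat does not settle how a missing component is handled.

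Two things are at stake. The first is precision: in a trial of 45, a few lost people matter, and a two-visit score is lost if either visit is lost. The 10% allowance is the same in Protocol 9.2, where the outcome is one visit, and in SAP 3.2, where it is two. The second is selection: if low Visit 5 readings were followed by missed Visit 6 assessments, people would leave the analysis because of the outcome itself, and more of them from the low sodium arm.

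**Working it through.** **1. The plan's own figures.** Inputs from SAP 3.2: difference 9.53 mm Hg, SD 10.46, alpha 0.05 (taken as two-sided, as in the planned test), power 80%, attrition 10%.

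- Normal approximation: n per arm = 2 × [10.46 × (1.960 + 0.842) / 9.53]² = 18.91, so 19.
- Exact two-sample t test: 19 per arm gives 78.0% and 20 per arm gives 80.2%. The stated 20 per arm reproduces.
- Recruitment: 40 / 0.9 = 44.4, so 45. This also reproduces.

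**2. How a single reading can arise.** SAP 3.1 needs readings on days 12-15.

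- Visit 5 or Visit 6 is missed.
- Visit 5 is held on day 10 or 11. Protocol 6.1 permits both days, 6.2.3 permits day 11, and 7.2 names day 10. Read strictly, such a person has one in-window reading without having missed anything.

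**3. Power if one-reading people are dropped.** Noncentral t with n per arm, noncentrality 9.53 / (10.46 × √(2/n)) and 2n − 2 degrees of freedom. For n = 20 the noncentrality is 9.53 / 3.308 = 2.88; for n = 18 it is 9.53 / 3.487 = 2.73. SAP 3.1 tests at 0.25, while Protocol 9.5 and the sample-size statement use 0.05, so both levels are shown.

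| Analysed | Power, alpha 0.05 | Power, alpha 0.25 |
|---|---|---|
| 40 | 80.2% | 95.6% |
| 38 | 78.0% | 94.9% |
| 36 | 75.7% | 94.0% |

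The documents give no loss rate per visit. Assuming 10% lost independently at each of the two visits, 45 × 0.9 × 0.9 = 36.5 people have both readings and 45 × (1 − 0.1 × 0.1) = 44.6 have at least one. In a simulation under that assumption (36.4 and 44.5 people on average), keeping one-reading people reduced the standard error of the treatment effect from 2.92 to 2.70 mm Hg, a cut of 0.22 / 2.92 = 7.5%. If instead only Visit 6 loses 10%, simulated power under the two-reading rule at alpha 0.05 is 80-81%.

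**4. Bias if low Visit 5 readings led to loss.** Simulated regression adjusted for baseline, 20 per arm, true effect −9.53, baseline limited to 100-149 mm Hg as in Protocol 4.1. Assumptions not in the documents: mean SBP before that selection 120-130, between-person SD 12-14, visit-to-visit SD 8-10. Everyone with a Visit 5 SBP below 90, the limit in Protocol 7.3, is taken to miss Visit 6.

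| Mean; SDs (between, visit) | Lost, low sodium / usual | All data | Two-reading completers |
|---|---|---|---|
| 130; 12, 8 | 1.3% / 0.1% | −9.50 | −9.34 |
| 125; 12, 8 | 2.6% / 0.3% | −9.58 | −9.26 |
| 120; 14, 10 | 7.5% / 1.7% | −9.45 | −8.58 |

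Across all six combinations run, the shift toward zero is about 0.2 to 0.9 mm Hg.

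**5. Which remedy recovers the effect.** In a separate simulation of the same loss pattern, two-reading completers gave −9.33 to −8.65, substituting the single available reading overshot at −9.58 to −9.83, and a random-intercept model on both visits gave about −9.50. The model does better because the loss depends on a reading that it uses.

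**The case against.** The strongest objection is that the documents nowhere require both readings or exclude a person with one. The SAP is silent, states intent-to-treat, keeps anyone with a final reading in its last-SBP sensitivity analysis, and plans imputation and best/worst-case checks. This stands in part: exclusion is an inference. It is still the natural one, because the primary model takes one value per person, and imputation and the last-reading analysis are only comparators to it.

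A reader might also infer that anyone taken off the diet after a low Visit 5 reading is automatically lost. The documents do not support that. Protocol 7.3 says stopping may be required, not that it must be, and stopping the diet is not leaving follow-up. Protocol 6.3, Protocol section 8 and SAP section 5 all plan continued measurement, and Visit 6 falls 1 to 4 days after Visit 5. If such people attend on Day 14, this selection does not arise.

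Third, the power loss rests on assumed losses. Recruiting 45 absorbs five losses of any kind before the number analysed falls below 40, and if dropouts miss both visits there are few one-reading people. At the SAP's 0.25 level the cost is under 2 points. All of this stands.

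Finally, one sentence telling the analyst to use the available reading would close the gap. It would, but that rule overshoots when the loss follows a low reading, and the repeated-measures model does not.

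**Conclusion.** The primary analysis lacks a rule for participants with one of the two SBPs, and as written they can be lost from it. That gap is in the text and needs no assumption.

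Its consequences are modest and conditional. At alpha 0.05, falling from 40 to 36 analysed costs 80.2 − 75.7 = 4.5 points of power; at 0.25 it costs 95.6 − 94.0 = 1.6 points. Reaching 36 requires about 10% loss at each visit, which the documents do not state. Bias toward zero requires both a low Visit 5 reading and a missed Visit 6. It is about 0.2 to 0.9 mm Hg on 9.53 even if everyone below 90 were lost, under assumed SBP distributions. The documents do not support a claim that the plan is underpowered or materially biased on this account. The case for changing it is that the rule should be fixed before analysis and that a better method is available at little cost.

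**What to change.** In SAP 3.1, replace the regression on the average with a repeated-measures linear model:

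- Outcomes: the Visit 5 and Visit 6 SBPs.
- Fixed effects for treatment, visit and baseline SBP, with a person-level random effect and a named small-sample degrees-of-freedom method.
- One treatment coefficient, averaged over both visits. For people with both readings this targets the same quantity as the planned average.
- Analysis set: everyone randomised with at least one follow-up SBP, whether or not still on the diet.

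Also reconcile the Visit 5 timing in Protocol 6.1, 6.2.3 and 7.2 with the days 12-15 of SAP 3.1 and the days 12 and 14 of SAP 4.2, and say how a reading outside the window is treated.

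The cost is SAP wording, a protocol clarification and a slightly more complex model, with no new data or visits. The downside is that one-reading participants contribute less precise information, which the model reflects in its weighting.

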## **Interventions and Duration**

Interventions for this study include:

1. A low sodium diet
2. A usual sodium diet

A participant will be on one of these two intervention arms for a period of 2 weeks. The last study visit for each participant will occur on the last day of their study diet intervention.

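### The protocol and the SAP define different primary endpoints, and the SAP's day window leaves out some permitted Visit 5 readings

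*SAP*

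**What the plan says.** **Endpoint.** Protocol 9.4.1 gives the primary outcome as "Seated systolic blood pressure measured during the follow-up visit". Protocol 6.1 and 6.2.4 place that visit, Visit 6, on Day 14, and the Synopsis adds: "The last study visit for each participant will occur on the last day of their study diet intervention". SAP 3.1 instead says "Our primary outcome will be the average of two systolic blood pressures measured on days 12-15 of the study period", followed by "A sensitivity analysis will be performed examining the last systolic blood pressure measurement". SAP 3.4 repeats the last-reading analysis as a sensitivity analysis. For diastolic pressure, SAP 4.2 specifies the "average of two measurements days 12 and 14".

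**Visit 5.** The schedule table in protocol 6.1 has "Treatment Visit 5 (Day 10-13", while protocol 6.2.3 has "Visit 5 (Intermediate Visit), Day 11-13". Protocol 7.2 places an on-study blood pressure check at day 10. The adverse event sections (7.3 and 7.5) give days 10 to 13.

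**Precedence.** Protocol 9.1 points to the SAP for further detail but does not say that the SAP replaces the protocol's endpoint. The version history records both documents going to the IRB on October 29, 2019, the date on the SAP, so neither is plainly the later one. Protocol section 8 lets visits move earlier or later and sets no limit.

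**The concern.** A primary endpoint should be one variable, fixed before the data are seen. Here the protocol's primary is in substance the SAP's sensitivity analysis. If the two results differ, either could be reported as planned.

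The two endpoints differ in timing as well as precision: one is SBP at the end of feeding, the other an average over the last few days.

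The SAP version also depends on which calendar days count. Visits 5 and 6 are the only scheduled seated blood pressure visits during feeding, so an average of two readings needs both. If a permitted Visit 5 falls outside the SAP window, that participant has one qualifying reading and the SAP does not say what to do. The choice would then be made at analysis, in a trial of about 40 people.

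**Working it through.** **1. The plan's own sample size.** Inputs from protocol 9.2 and SAP 3.2: difference 9.53 mm Hg, SD 10.46, type 1 error 0.05, power 80%. The test is taken as two-sided, as in protocol 9.5.

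- Normal approximation: n per arm = 2 × [10.46 × (1.9600 + 0.8416) / 9.53]² = 18.91, so 19.
- Two-sample t-test: 19.92, so 20. Power at 20 per arm is 80.2%.
- Attrition: 40 / (1 − 0.10) = 44.4, so 45.

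The stated 20, 40 and 45 reproduce.

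**2. The endpoints side by side.**

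| | Protocol 9.4.1 | SAP 3.1 |
|---|---|---|
| Primary | SBP at Visit 6 | Mean of two SBPs, days 12 to 15 |
| Last SBP alone | Primary | Sensitivity |

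The protocol does not say how many cuff readings are taken at a visit, so its endpoint is one visit, not necessarily one reading.

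**3. Visit 5 days outside the SAP window.**

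| Source of Visit 5 timing | Same day numbering | Protocol Day 0 = SAP day 1 |
|---|---|---|
| Protocol 6.1, 7.3, 7.5 (Days 10 to 13) | Days 10 and 11 | Day 10 |
| Protocol 6.2.3 (Days 11 to 13) | Day 11 | None |
| Protocol 7.2 (day 10) | Day 10 | Day 10 |

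No constant shift in numbering rescues Day 10. Days 10 and 14 are 4 days apart, while days 12 and 15 are 3 apart, so one window cannot hold both a Day 10 Visit 5 and a Day 14 Visit 6. The one-day shift is also hard to square with SAP 4.2: its days 12 and 14 would become protocol Days 11 and 13, and neither is Visit 6.

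**4. Share of participants affected.** The documents give no distribution of Visit 5 dates. If all fall on day 12, as SAP 4.2 implies, the share is 0%. If all fall on day 10, as protocol 7.2 suggests, it is 100%.

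**5. What averaging gains.** Let a be the correlation of baseline with each follow-up reading and b the correlation between the two follow-up readings. The documents give neither. After adjustment for one baseline reading, residual variance in units of one reading's variance is 1 − a² for a single reading and (1 + b)/2 − a² for the mean of two.

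| a | b | Ratio, mean to single | Reduction |
|---|---|---|---|
| 0.5 | 0.5 | 0.50 / 0.75 = 0.667 | 33% |
| 0.6 | 0.6 | 0.44 / 0.64 = 0.688 | 31% |
| 0.7 | 0.7 | 0.36 / 0.51 = 0.706 | 29% |
| 0.5 | 0.8 | 0.65 / 0.75 = 0.867 | 13% |
| 0.6 | 0.9 | 0.59 / 0.64 = 0.922 | 8% |

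Readings a few days apart may well correlate more strongly than either does with baseline, which favours the lower rows.

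**6. Effect on power.** Assume SD 10.46 belongs to one reading and ignore baseline adjustment. The SD of the mean is 10.46 × √[(1 + b)/2].

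| b | SD of mean | t-test n per arm | Power at 20 per arm |
|---|---|---|---|
| 0.5 | 9.06 | 16 | 90% |
| 0.7 | 9.64 | 18 | 86% |
| 0.9 | 10.20 | 19 | 82% |

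With two readings for everyone, power is at or above the planned 80%.

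**The case against.** The best defence is that the SAP names one primary analysis and pre-specifies the last reading as a sensitivity analysis, and that protocol 9.1 refers to the SAP, so an analyst would follow the SAP. This softens the conflict but does not remove it: the reference is for detail only, and protocol 9.4.1 still states a different endpoint.

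A second defence is day numbering. Counting protocol Day 0 as SAP day 1 turns days 12 to 15 into protocol Days 11 to 14, which fits protocol 6.2.3 plus Visit 6 exactly. That would settle Day 11 and Day 15, but not Day 10, and SAP 4.2 speaks against it.

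Three stronger readings are tempting but go beyond the documents:

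- A reader might infer that half the participants (2 of 4 permitted days) or a third (1 of 3) lose a reading. Those figures require evenly spread visit dates, which nothing supports.
- A reader might infer that day 15 brings off-diet pressures into the endpoint. The Synopsis puts the last visit on the last diet day, so this could happen only through the open-ended visit flexibility in protocol section 8.
- A reader might infer that participants with one qualifying reading would be dropped. The SAP has no such rule; it specifies intention-to-treat and missing-data sensitivity analyses. What stands is that no rule is given.

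**Conclusion.** The concern holds as a contradiction in the definition of the primary endpoint, with a related mismatch between the SAP window and the visit schedule. It needs correcting because it determines which readings enter the primary analysis and which result is called primary.

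The endpoint conflict and the exclusion of Day 10 rest on the text alone. The exclusion of Day 11 assumes that both documents number days alike, which SAP 4.2 supports.

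The size is uncertain. The affected share is unknown, and the 8% to 33% variance reduction is a range over assumed correlations; quoting only its upper end, 29% to 33%, would require one common correlation for all pairs of readings. A reader might also conclude that the sample size is wrong. It is not: the stated figure reproduces, and averaging two readings can only help precision if SD 10.46 refers to one.

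**What to change.** State one primary endpoint in both documents, identified by visit and not by calendar day: the mean of the Visit 5 and Visit 6 seated SBP, for all randomised participants regardless of diet adherence or discontinuation. If one reading is missing, use the other. Keep Visit 6 alone as the sensitivity analysis. Do not require the readings to be taken on diet, since that would conflict with the plan to follow participants who stop the intervention.

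Amend protocol 9.4.1 to match. Reconcile Visit 5 timing and day numbering across protocol 6.1, 6.2.3, 7.2, 7.3 and 7.5 and SAP 3.1 and 4.2; which days apply is for the investigators to settle.

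The cost is wording, since both readings are already scheduled. The downside is that a participant with one reading contributes a somewhat noisier outcome. The change should be made before outcome data are analysed by arm.
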